16.10.6. Efficacy Figures

Efficacy: Figures					
No.	Population	IDSL / Example Shell	Title	Programming Notes	Deliverable
HES Flare					
2.1.	ITT	EFF_F1	Cumulative Number of HES Flares		Headline
2.2.	ITT	EFF_F2	Analysis of Proportion of Subjects with HES Flare During the 32-Week Treatment Period	Present odds ratios and 95% CI from 5 analyses of the primary endpoint on one figure: Primary estimand, While on treatment estimand, Per protocol population, Alternative missing data imputation strategy #1, Alternative missing data imputation strategy #2.	Headline
2.3.	ITT	EFF_F3	Kaplan-Meier Cumulative Incidence Curve for Time to First HES Flare		SAC
2.4.	ITT	EFF_F2	Analysis of Time to First HES Flare (Treatment Policy Estimand)	Present relative risk and 95% CI from 3 analyses corresponding to 3 missing data imputation strategies: Primary estimand, Alternative missing data imputation strategy #1, Alternative missing data imputation strategy #2	SAC
2.5.	ITT	-	Exploratory Modelling of Proportion of Subjects with HES Flare During the 32-Week Treatment Period vs Baseline Blood Eosinophils		SAC
2.6.	ITT	EFF_F2	Analysis of Proportion of Subjects with HES Flare During Week 20 Through Week 32 (Treatment Policy Estimand)	Present odds ratio and 95% CI from 3 analyses corresponding to 3 missing data imputation strategies: Primary estimand, Alternative missing data imputation strategy #1, Alternative missing data imputation strategy #2	SAC

Efficacy: Figures					
No.	Population	IDSL / Example Shell	Title	Programming Notes	Deliverable
2.7.	ITT	EFF_F2	Analysis of Rate of HES Flare (Treatment Policy Estimand)	Present rate ratio and 95% CI from two analyses: Primary estimand, Jump to reference	SAC
Worst Level of Fatigue in Past 24 Hours (BFI Item 3)					
2.8.	ITT	EFF_F6	Cumulative Distribution Plot for the Change from Baseline in Mean Daily Fatigue Severity - Worst Level of Fatigue in Past 24 Hours (BFI Item 3) – at Week 32		SAC
2.9.	ITT	EFF_F4	Change from Baseline in Fatigue Severity - Worst Level of Fatigue in Past 24 Hours (BFI Item 3) (Treatment Policy Estimand, Mixed Model Repeated Measures)	Present adjusted mean (95% CI) change from baseline by time (weeks) from repeated measures model – Week 0, 4, 8, 12, 16, 20, 24, 28, 32. Add footnote: “Note: Adjusted for baseline (week 0) BFI item 3 score and region”.	SAC
2.10.	ITT	EFF_F5	Change from Baseline in Fatigue Severity - Worst Level of Fatigue in Past 24 Hours (BFI Item 3) - Treatment Difference vs Placebo (Treatment Policy Estimand, Mixed Model Repeated Measures)	Present adjusted mean treatment difference (95% CI) change from baseline by time (weeks) from repeated measures model – Week 0, 4, 8, 12, 16, 20, 24, 28, 32. Add footnote: “Note: Adjusted for baseline (week 0) BFI item 3 score and region”.	SAC
FEV1 and FVC					
2.11.	ITT	EFF_F4	Change from Baseline in FEV 1 (Treatment Policy Estimand, Mixed Model Repeated Measures)		SAC
2.12.	ITT	EFF_F5	Change from Baseline in FEV 1 - Treatment Difference vs Placebo (Treatment Policy Estimand, Mixed Model Repeated Measures)		SAC

Efficacy: Figures					
No.	Population	IDSL / Example Shell	Title	Programming Notes	Deliverable
2.13.	ITT	EFF_F4	Change from Baseline in FVC (Treatment Policy Estimand, Mixed Model Repeated Measures)		SAC
2.14.	ITT	EFF_F5	Change from Baseline in FVC - Treatment Difference vs Placebo (Treatment Policy Estimand, Mixed Model Repeated Measures)		SAC
HES Symptom Severity (HES-DS)					
2.15.	ITT	EFF_F4	Change from Baseline in Most Bothersome HES Symptom Severity Score (HES-DS) (Treatment Policy Estimand, Mixed Model Repeated Measures)	Present adjusted mean (95% CI) change from baseline by time (weeks) from repeated measures model – Week 0, 4, 8, 12, 16, 20, 24, 28, 32. Add footnote: “Note: Adjusted for baseline (week 0) most bothersome symptom score and region”.	SAC
2.16.	ITT	EFF_F5	Change from Baseline in Most Bothersome HES Symptom Severity Score (HES-DS) - Treatment Difference vs Placebo (Treatment Policy Estimand, Mixed Model Repeated Measures)	Present adjusted mean treatment difference (95% CI) change from baseline by time (weeks) from repeated measures model – Week 0, 4, 8, 12, 16, 20, 24, 28, 32. Add footnote: “Note: Adjusted for baseline (week 0) most bothersome symptom score and region”.	SAC
2.17.	ITT	EFF_F4	Change from Baseline in HES Symptom Severity Score (HES-DS) by Symptom (Treatment Policy Estimand, Mixed Model Repeated Measures)	One page per domain with byline. Present adjusted mean (95% CI) change from baseline by time (weeks) from repeated measures model – Week 0, 4, 8, 12, 16, 20, 24, 28, 32. Add footnote: “Note: Adjusted for baseline (week 0) symptom score and region”.	SAC

Efficacy: Figures					
No.	Population	IDSL / Example Shell	Title	Programming Notes	Deliverable
2.18.	ITT	EFF_F5	Change from Baseline in HES Symptom Severity Score (HES-DS) by Symptom - Treatment Difference vs Placebo (Treatment Policy Estimand, Mixed Model Repeated Measures)	One page per domain with byline. Present adjusted mean treatment difference (95% CI) change from baseline by time (weeks) from repeated measures model – Week 0, 4, 8, 12, 16, 20, 24, 28, 32. Add footnote: “Note: Adjusted for baseline (week 0) symptom score and region”.	SAC
Weekly Fatigue Severity – BFI Total Scores					
2.19.	ITT	EFF_F4	Change from Baseline in Total BFI Score (Treatment Policy Estimand, Mixed Model Repeated Measures)	Present adjusted mean (95% CI) change from baseline by time (weeks) from repeated measures model – Week 0, 4, 8, 12, 16, 20, 24, 28, 32. Add footnote: “Note: Adjusted for baseline (week 0) total BFI score and region”.	SAC
2.20.	ITT	EFF_F5	Change from Baseline in Total BFI Score - Treatment Difference vs Placebo (Treatment Policy Estimand, Mixed Model Repeated Measures)	Present adjusted mean treatment difference (95% CI) change from baseline by time (weeks) from repeated measures model – Week 0, 4, 8, 12, 16, 20, 24, 28, 32. Add footnote: “Note: Adjusted for baseline (week 0) total BFI score and region”.	SAC
Modified Memorial Symptom Assessment Scale-Short Form (MSAS-SF)					

Efficacy: Figures					
No.	Population	IDSL / Example Shell	Title	Programming Notes	Deliverable
2.21.	ITT	EFF_F4	Change from Baseline in MSAS-SF Total and Subscale Scores (Treatment Policy Estimand, Mixed Model Repeated Measures)	
One plot per page, 4 pages with by line: Total MSAS-SF Score, MSAS-SF Global Distress Index, MSAS-SF Physical Subscale Score, MSAS-SF Psychological Subscale Score.
 
Present adjusted mean (95% CI) change from baseline by time (weeks) from repeated measures model – Week 0, 4, 8, 16, 24, 32.
 
Add footnote: “Note: Adjusted for baseline (week 0) score and region. Scale: 0 = Not at all distressed or bothered/No symptoms to 4 = Very much distressed or bothered/Almost constant symptoms.”
	SAC

Efficacy: Figures					
No.	Population	IDSL / Example Shell	Title	Programming Notes	Deliverable
2.22.	ITT	EFF_F5	Change from Baseline in MSAS-SF Total and Subscale Scores - Treatment Difference vs Placebo (Treatment Policy Estimand, Mixed Model Repeated Measures)	
Either one plot per page, 4 pages with by line, or 4 lines on one plot, as data permit: Total MSAS-SF Score, MSAS-SF Global Distress Index, MSAS-SF Physical Subscale Score, MSAS-SF Psychological Subscale Score.
 
Present adjusted mean treatment difference (95% CI) change from baseline by time (weeks) from repeated measures model – Week 0, 4, 8, 12, 16, 20, 24, 28, 32.
 
Add footnote: “Note: Adjusted for baseline (week 0) score and region. Scale: 0 = Not at all distressed or bothered/No symptoms to 4 = Very much distressed or bothered/Almost constant symptoms.”
	SAC

Efficacy: Figures					
No.	Population	IDSL / Example Shell	Title	Programming Notes	Deliverable
PROMIS Physical Function and Sleep					
2.23.	ITT	EFF_F4	Change from Baseline in PROMIS Physical Function and Sleep Score (Treatment Policy Estimand, Mixed Model Repeated Measures)	
One plot per page, 2 pages with by line: PROMIS Physical Function Score, PROMIS Sleep Score.
 
Present adjusted mean (95% CI) change from baseline by time (weeks) from repeated measures model – Week 0, 4, 8, 16, 24, 32.
 
Add footnote: “Note: 1. Adjusted for baseline (week 0) score and region. 2. Sleep score scale 1 = Not at all difficulty in falling asleep /Never trouble staying asleep to 5 = Very much difficulty in falling asleep /Always trouble staying asleep. 3. Physical function scale 0 = Not at all distressed or bothered/No symptoms to 4 = Very much distressed or bothered/Almost constant symptoms.”
	SAC

Efficacy: Figures					
No.	Population	IDSL / Example Shell	Title	Programming Notes	Deliverable
2.24.	ITT	EFF_F5	Change from Baseline in PROMIS Physical Function and Sleep Score - Treatment Difference vs Placebo (Treatment Policy Estimand, Mixed Model Repeated Measures)	
Either one plot per page, 2 pages with by line, or 2 lines on one plot, as data permit: PROMIS Physical Function Score, PROMIS Sleep Score.
 
Present adjusted mean treatment difference (95% CI) change from baseline by time (weeks) from repeated measures model – Week 0, 4, 8, 16, 24, 32.
 
Add footnote: “Note: 1. Adjusted for baseline (week 0) score and region.
 
2. Sleep score scale 1 = Not at all difficulty in falling asleep /Never trouble staying asleep to 5 = Very much difficulty in falling asleep /Always trouble staying asleep.
 
3. Physical function scale 0 = Not at all distressed or bothered/No symptoms to 4 = Very much distressed or bothered/Almost constant symptoms.”
	SAC

**16.10.7. Health Outcomes Tables**

Health Outcomes: Tables					
No.	Population	IDSL / Example Shell	Title	Programming Notes	Deliverable
SF-36					
3.1.	ITT	EFF_T6	Summary of SF-36 Health Survey Domain Scores	Include change from baseline values. Include 95% CIs for the mean.	SAC
3.2.	ITT	EFF_T6	Summary of SF-36 Health Survey Component Summary Scores	Include change from baseline values Include 95% CIs for the mean.	SAC
Healthcare Resource Utilisation					
3.3.	ITT	EFF_T14	Summary of Healthcare Resource Utilisation Associated with HES Flare		SAC
Work Productivity and Activity Impairment Questionnaire					
3.4.	ITT	EFF_T15	Summary of Work Productivity and Activity Impairment		SAC

**16.10.8. Safety Tables**

No.	Population	IDSL / Example Shell	Title	Programming Notes	Deliverable
Adverse Event Overview					
4.1.	Safety	SAFE_T1	Adverse Event Overview		SAC
Adverse Events					
4.2.	Safety	AE1	Summary of All On-Treatment Adverse Events by System Organ Class and Preferred Term		SAC
4.3.	Safety	AE1	Summary of All Post-Treatment Adverse Events by System Organ Class and Preferred Term		SAC
4.4.	Safety	AE3	Summary of Common ( $\geq 3\%$ Incidence) On-Treatment Adverse Events by Overall Frequency		SAC
4.5.	Safety	AE15	Summary of Common ( $\geq 3\%$ Incidence) On-Treatment Non-Serious Adverse Events by System Organ Class and Preferred Term (Number of Subjects and Occurrences)		SAC
4.6.	Safety	AE5A	Summary of All On-Treatment Adverse Events by Maximum Intensity by System Organ Class and Preferred Term		SAC
4.7.	Safety	AE1	Summary of All Drug-Related Adverse Events by System Organ Class and Preferred Term		SAC
4.8.	Safety	AE5A	Summary of All Drug-Related Adverse Events by Maximum Intensity by System Organ Class and Preferred Term		SAC
4.9.	Safety	AE1	Summary of Non-Serious Drug-Related Adverse Events by System Organ Class and Preferred Term		SAC
4.10.	Safety	AE1	Summary of On-Treatment Adverse Events by Highest Post-Baseline Binding Antibody Result	Add in row with n in each binding antibody result category.	SAC

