4.2. Treatment Arms and Duration

- The study is comprised of a screening period of up to approximately 4 weeks followed by a 32-week study treatment period and up to 8-week additional follow-up period (12 weeks after the last dose of study treatment).
- Approximately 80 subjects who are able to maintain a stable regimen of HES therapy for the 4 weeks prior to Visit 2 will be randomized in a 1:1 ratio to receive either 300 mg mepolizumab *or* placebo SC every 4 weeks while continuing their HES therapy. The sample size may be increased up to a maximum of 120 subjects in total (Section 9.2.3). The same regimen of HES therapy will be maintained throughout the 32-week study treatment period unless there is worsening of symptom(s) that requires an increase in therapy. A reduction in dose for safety reasons, with return to the original dosing regimen if possible, is permitted in consultation with the GSK Medical Monitor.

- The final dose of study treatment will be administered at Visit 10 (Week 28) with completion of the study treatment period achieved at the next 4-weekly visit. At Visit 11 (Week 32), subjects will complete the end-of-treatment assessment (4 weeks after the last dose).
- Subjects who withdraw from study treatment prematurely should continue in the study per protocol (including HES flare-related assessments) until 32 weeks from randomization.
- For subjects whose last dose of study treatment is on Visit 9 (Week 24) or Visit 10 (Week 28) *and* who do not continue with open-label mepolizumab after completing Visit 11 assessment (32 weeks from randomization), there will be up to 8-week additional follow-up period, concluding with the 12 weeks post-last dose follow-up visit (Visit 12).
- Subjects will be eligible to be considered to receive open-label mepolizumab 300 mg SC every 4 weeks after *either*:
 - i. Completion of the treatment period in the 200622 study
 - or*
 - ii. If the subject was withdrawn from study treatment prematurely during the 200622 study, but continued in the study per protocol (including HES flare-related assessments) until 32 weeks from randomization.

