	
mepolizumab combined.
 
A review of a well established cohort of patients with hyper eosinophilia including those with HES at the Mayo clinic showed that 5.1% developed hematologic malignancy over 13-year period; the median time the malignancy developed was 10 months after the onset of hyper eosinophilia. T-cell derived malignancies were most commonly diagnosed [Jin, 2015].
 
 • Malignancies, including lymphoma, reported to date across the mepolizumab program (severe asthma and HES) are summarized in the IB; see also 'Special Warnings and Special Precautions for Use' section located in IB Section 6 titled 'Summary of Data and Guidance for the Investigator'. 	
Potential risk for exaggerated response of symptoms upon cessation of treatment	
 • No apparent rebound eosinophilia observed in monkeys treated with mepolizumab. • Across the PCSA program, post-treatment AEs of asthma did not appear to occur at a significantly greater incidence following cessation of treatment with mepolizumab compared with placebo. 	
 • Daily monitoring of SAEs by GSK Medical Monitor; regular systematic review of AE/SAE data from ongoing studies by a GSK safety review team • An IDMC will be utilized during study.
Study Procedures		
Blinding eosinophil counts	
 • This study is a double-blind study which will be used to support approval of the use of mepolizumab in the treatment of HES. Unblinding eosinophil counts would compromise the integrity of the study. 	
 • An IDMC will be utilized during study. • Blood eosinophil-unblinded GSK personnel/delegates not involved with other aspects of study conduct will monitor the absolute eosinophil count results and trigger blinded OCS treatment to treat an eosinophilia flare (Section 6.4).

Potential Risk of Clinical Significance	Data/Rationale for Risk	Mitigation Strategy
		Investigators, participating subjects, and GSK study personnel will be blinded to absolute blood eosinophil counts, total white blood cell count, and white blood count differentials (%) from randomization to the end of the study.

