Safety	
 
All subjects who are randomised and who receive at least one dose of study treatment. Randomised subjects will be assumed to have received study treatment unless definitive evidence to the contrary exists.
 
This population will be based on the treatment the subject actually received.
 
Subjects will be analysed according to treatment received for more than 50% of their treatment administrations. If a subject received an equal number of both treatments then they will be assigned to the treatment to which they were randomised.
 
	
 
Study Population
 
Safety
 

Pharmacokinetic	
 
All subjects in the ITT population who received
 
	
 
PK
 

Population	Definition / Criteria	Analyses Evaluated
	at least one dose of study treatment and for whom at least one PK sample was obtained, analysed and was measurable.	
Pharmacodynamic	
 
• All subjects in the ITT population who received at least one dose of study treatment and who also had a baseline PD measurement and at least one post-treatment PD measurement.
 
	
 
• PD
 

Refer to [Appendix 10](#): List of Data Displays which details the population used for each display.

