## 11. SAFETY ANALYSES

The safety analyses will be based on the Safety population, unless otherwise specified.

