### 16.4.4. Treatment Phases for Adverse Events

Study Phase	Definition
Pre-Treatment	AE onset date/time < Date/time of first dose of study treatment
On-Treatment	Date/time of first dose of study treatment ≤ AE onset date/time ≤ Date of last dose of study treatment + 28 days
Post-Treatment	AE onset date > Date of last dose of study treatment + 28 days

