**CONFIDENTIAL**

200622

No.	Population	IDSL / Example Shell	Title	Programming Notes	Deliverable
4.11.	Safety	AE3	Summary of All Adverse Events Leading to Permanent Discontinuation from Study Treatment by Overall Frequency		SAC
4.12.	Safety	AE3	Summary of All Adverse Events Leading to Withdrawal from the Study by Overall Frequency		SAC
4.13.	Safety	AE1	Summary of Adverse Events Reported on the Day of Dosing by System Organ Class and Preferred Term		SAC
4.14.	Safety	AE7	Listing of Subject Numbers for Individual On-Treatment Adverse Events		SAC
4.15.	Safety	AE7	Listing of Subject Numbers for Individual Post-Treatment Adverse Events		SAC
4.16.	Safety	AE2	Listing of Relationship of Adverse Event, System Organ Classes, Preferred Terms and Verbatim Text		SAC
Serious Adverse Events					
4.17.	Safety	AE3	Summary of Fatal Serious Adverse Events by Overall Frequency		Headline
4.18.	Safety	AE3	Summary of Drug-Related Fatal Serious Adverse Events by Overall Frequency		SAC
4.19.	Safety	AE3	Summary of Non-Fatal Serious Adverse Events by Overall Frequency		SAC
4.20.	Safety	AE3	Summary of All Serious Adverse Events by Overall Frequency		Headline
4.21.	Safety	AE1	Summary of All On-Treatment Serious Adverse Events by System Organ Class and Preferred Term		SAC
4.22.	Safety	AE1	Summary of All Post-Treatment Serious Adverse Events by System Organ Class and Preferred Term		SAC

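### Tables 4.3 and 4.22 give post-treatment AE and SAE percentages on the whole Safety population, although post-treatment observation ranges from 0 to 196 days depending on how a subject left treatment

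*SAP*

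**What the plan says.** SAP 16.4.4 defines the post-treatment phase for adverse events as "AE onset date > Date of last dose of study treatment + 28 days", with no upper limit. SAP 16.10.8 plans "Summary of All Post-Treatment Adverse Events by System Organ Class and Preferred Term" (Table 4.3) and "Summary of All Post-Treatment Serious Adverse Events by System Organ Class and Preferred Term" (Table 4.22). Both have Safety in the population column and an empty programming note. SAP 11 sets the default: "The safety analyses will be based on the Safety population, unless otherwise specified". SAP 4 defines that population as "All subjects who are randomised and who receive at least one dose of study treatment", with no requirement to have been observed after treatment.

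Protocol 4.2 puts the final dose at Week 28. The extra follow-up to 12 weeks after the last dose applies to subjects whose last dose was at Week 24 or 28 and "who do not continue with open-label mepolizumab after completing Visit 11 assessment". Subjects who do continue have their last assessment at Week 32 (SAP 2.2). Subjects who stop treatment early stay in the study to Week 32 where possible, and may then also enter open-label treatment. AEs are collected up to the follow-up contact (Protocol 7.4.1.1). The risk table in Protocol 4.6.1 names "Potential risk for exaggerated response of symptoms upon cessation of treatment".

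**The concern.** A percentage on the full Safety population treats every subject as equally able to show a post-treatment event. Here that ability depends on the route out of treatment. A completer who goes straight into the open-label study is hardly observed after day 28 but counts as event-free. A subject who stopped after the first dose and stayed in the study is observed for months.

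Tables 4.3 and 4.22 are the only planned summary tables specific to this phase, and stopping treatment is a risk the protocol names. A low percentage could be read as reassurance when it reflects absent follow-up. If early stopping or open-label uptake differs between arms, the percentages will differ even when the underlying risk is the same.

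**Working it through.** **Inputs from the documents.** Last dose for completers: Week 28, day 196 after first dose (Protocol 4.2). Phase boundary: last dose + 28 days (SAP 16.4.4). Nominal Week 32: first dose + 224 days (SAP 16.6.1). Visit 12: last dose + 84 days. Visit windows: ±7 days (Protocol 7.1). Planned size: 40 per arm (Protocol 9.2.1).

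**Assumed, because the documents give no values.** R, the true risk over 56 post-treatment days; f, the share of completers entering open-label; the share stopping early; and a constant hazard.

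**1. The plan's own figure.** The boundary is 196 + 28 = day 224, and Visit 12 is 196 + 84 = day 280. The difference is 56 days, which reproduces the stated additional follow-up of up to 8 weeks.

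**2. Post-treatment days by route.**

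| Route | Days |
|---|---|
| Completer entering open-label | 224 − 224 = 0 nominal; at most 231 − (189 + 28) = 14 |
| Completer not entering | 56 |
| Stopper, last dose Week 24 | 224 − (168 + 28) = 28 if entering open-label; 56 if not |
| Stopper, last dose Week 20, 16, 12, 8, 4, 0, followed to Week 32 | 56, 84, 112, 140, 168, 196 |

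**3. Effect of roll-over alone.** Let Visits 10 and 11 fall independently and uniformly on whole days within ±7. The mean of max(0, V11 − V10 − 28) is then 560/225 = 2.5 days, and 105/225 = 47% of entrants have at least one post-treatment day. The hazard is λ = −ln(1 − R)/56. For R = 30%, λ is 0.00637 per day (2.33 per subject-year) and an entrant's mean risk m is 1.55%. With no early stoppers, the table shows (1 − f)R + f·m:

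| R | f = 50% | f = 80% | f = 95% |
|---|---|---|---|
| 10% | 5.2% | 2.4% | 0.9% |
| 20% | 10.5% | 4.8% | 1.9% |
| 30% | 15.8% | 7.2% | 3.0% |

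**4. Early stoppers push the other way.** Take R = 30% and 20% stoppers averaging 126 days, the mean of the six values from 56 to 196. Their risk is 1 − 0.7^(126/56) = 55.2%.
- If 80% of completers roll over: 0.2 × 55.2 + 0.8 × 7.2 = 16.8%.
- If none roll over: 0.2 × 55.2 + 0.8 × 30 = 35.0%, above the true 30%.

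**5. Arm difference with no true difference.** Take R = 30%, 40 per arm and all completers rolling over. Suppose 2 subjects in one arm and 8 in the other stop after the Week 8 dose (140 days; risk 1 − 0.7^(140/56) = 59.0%).
- Table percentages: (2 × 59.0 + 38 × 1.55)/40 = 4.4% and (8 × 59.0 + 32 × 1.55)/40 = 13.0%.
- Subject-time: 2 × 140 + 38 × 2.49 = 375 days and 8 × 140 + 32 × 2.49 = 1,200 days.
- Expected rate: 2.33 per subject-year in both arms.

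**6. A simpler remedy that does not work.** Restrict the denominator to subjects with any contact after last dose + 28 days. The 47% of entrants with a few days remain, and the percentage becomes [(1 − f)R + f·m]/[(1 − f) + 0.467f]. For R = 30% this gives 21.5%, 12.6% and 6.0% at f = 50%, 80% and 95%, still far from 30%.

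**The case against.** No test or relative risk is planned on these two tables. The SAE and special-interest comparison (Table 4.26) is on-treatment, a phase that already includes the 28 days after the last dose. Post-treatment events also appear in Table 4.15, in the listings that carry study phase, and in all-phase tables such as 4.20 and 4.24, so a reader who inferred that nothing else bears on events after stopping would be wrong. Disposition Tables 1.1 and 1.2 count open-label entrants and treatment discontinuations. The stated mitigation for the cessation risk is SAE monitoring, safety team review and the IDMC. Expected disease symptoms are not AEs unless more severe than expected (Protocol 12.4.1), and flares have their own off- and post-treatment phases (SAP 16.4.1). The AE1 shell is not shown, so the denominator is inferred. Any split by follow-up route rests on decisions made after randomisation, so the arms within a route are not randomised groups.

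All of this stands, and it limits the point to how two descriptive tables are read. None of these outputs gives a post-treatment rate or the time behind it. The off-treatment time in SAP 16.6.1 is not linked to these tables and stops at Week 32.

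Two stronger readings also fail. One is that the percentages must understate the risk; step 4 shows they can overstate it. The other is that subjects who roll over are missing intended follow-up. Protocol 4.2 and 5.5 require the extra 8 weeks only of those who do not continue.

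**Conclusion.** The point holds as a cheap improvement to two descriptive safety tables. Each percentage pools subjects with 0 to 196 post-treatment days and counts unobserved subjects as event-free. Neither the direction nor the size of the distortion can be fixed from the documents. At an assumed 8-week risk of 30%, the illustrations run from 3.0% (95% roll-over, no stoppers) to 35.0% (no roll-over, 20% stoppers). An arm contrast of 4.4% against 13.0% can arise from early stopping alone. These figures rest on a constant hazard, uniform visit timing, stoppers followed to Week 32, and the Safety population being the displayed denominator. Efficacy and on-treatment safety conclusions are not affected.

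**What to change.** Keep the existing counts in Tables 4.3 and 4.22 and add, by arm:
- the number of subjects observed beyond last dose + 28 days;
- total post-treatment subject-time, from that date to the last study contact, including Visit 12;
- events per subject-year.

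Show these separately for completers entering open-label, completers not entering, and early treatment stoppers. Do not rely on a percentage among subjects with any contact after last dose + 28 days (step 6).

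The cost is one derived duration and a programming note. No new data are needed, because Table 1.1 already separates open-label entrants from follow-up completers, and Table 4.10 already adds a row of group sizes. The downside is a little more programming and small groups with imprecise rates. The rates should be labelled descriptive because the groups are formed after randomisation.
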